We have chosen a modified stepped wedge trial design for the following reasons: (1) we predict that the intervention will do more good than harm and (2) for logistical reasons, it is not practical to deliver the intervention simultaneously to all participants. Rolling out the intervention in a staggered fashion will ensure that there is adequate time for individual site preparation and staff training, as well as oversight of study activities. Before study initiation, the six participating clinics will be randomized to observation and intervention periods, as presented below in Figure 2.

Version 1.1 17 July 2018 Page 23 of 137

Figure 2. Stepped Wedge Design at Six Sites

. iguit zi etoppeu rreuge zeoigii ut eix eitee								
Clinic	0-3	4-6	7-9	10-12	13-15	16-18	19-21	22-24
Site 1	0	_						
Site 2	0	0	1	I				
Site 3		0	0	ı	ı			
Site 4			0	0	ı	ı		
Site 5				0	0	I	I	
Site 6					0	0	ı	ı
N enrolled	250	375	500	500	500	375	250	125

I = intervention period, N = number, O = observation period

Randomization will be performed using a random number generator to assign each clinic to one of the six positions, with stratification by facility type (public vs. private). Due to practical limitations, allocations will be unblinded. We will recruit 125 participants per clinic per 3-month time block, for 2,875 total participants (1,375 in the observation period and 1,500 in the intervention period) in the HIV-1 RNA testing intervention. By the end of the trial, each facility will have undergone an observation period of 3-6 months and received the intervention for 3-6 months. Thus, each health facility or "cluster" will act as its own control, with comparison of those patients enrolled during the observation period to those patients enrolled during the intervention period. Using this design, we can model the effect of time on the intervention, adjusting for temporal variations in HIV incidence [56, 57].

Version 1.1 17 July 2018 Page **24** of **137**

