14. SAMPLE SIZE CONSIDERATIONS

The proposed work is powered for the stepped wedge design (Figure 2). Based on our pilot work, we estimate that 50%-60% of adults aged 18-39 at the six participating facilities will be eligible for the study and approximately 50%-80% of these will accept study participation. Our preliminary data shows that approximately 2% of young adults in this age range are diagnosed with prevalent HIV-1 infection under standard care, while approximately 5% will be newly diagnosed with acute (1%) or prevalent (4%) HIV-1 infection in the intervention period. If these estimates are correct, with 1,375 subjects in the observation period and 1,500 subjects in the intervention period and a type I error probability of 0.05, assuming a coefficient of variation (k) of 0.25, we will have >90% power to reject the null hypothesis that the HIV diagnosis rates for experimental and control subjects are equal [57]. This power is more than adequate for multivariable analysis related to the testing of this null hypothesis. Because facilities will not have the laboratory capacity to diagnose HIV before seroconversion during the observation period, the base rate of AHI detection is 0, and power to detect AHI during the intervention period is >90% even if AHI prevalence is well below 1%. The table below presents power for a range of coefficients of variation and acute/prevalent HIV prevalence in the intervention period, given our chosen sample size.

Table. Power for Evaluation of Null Hypothesis that HIV Diagnosis Rates are Equal

Diagnosed HIV, Observation Period	Diagnosed HIV, Intervention Period	Kappa	Power
2.0%	5.0%	0.20	94.4%
2.0%	4.3%	0.20	82.2%
2.0%	5.0%	0.25	93.0%
2.0%	4.3%	0.25	80.0%
2.0%	5.0%	0.30	91.4%
2.0%	4.3%	0.30	77.3%
2.0%	5.0%	0.35	89.4%
2.0%	4.3%	0.35	74.6%

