15. DATA ANALYSIS

15.1. HIV Testing Uptake and Diagnoses

We will compare the age and sex of individuals who accept vs. refuse screening, using Student t and Chi-square tests. In addition, we will tally reasons for refusal to participate among those eligible, and compare eligible individuals who refuse vs. consent to study enrolment, using Chi-square or Fisher exact tests for categorical variables and Student t tests or Mann-Whitney U tests for continuous variables. Proportions of individuals who accept screening, are determined eligible, and enroll will be presented, with exact binomial CI.

We will compare the proportion of patients with the following outcomes in the observation and intervention periods: (1) tested for HIV infection; (2) newly diagnosed with prevalent HIV infection (i.e., HIV seropositive); (3) newly diagnosed with AHI. Because we expect 0 AHI cases in the observation period, we will use a combined outcome (i.e., newly diagnosed acute or prevalent HIV-1) to model the effect of the intervention, so that models will converge. We will conduct analyses on the individual-level data, using log-binomial generalized estimating equation (GEE) models to account for clustering by health facility. We will use a small-sample variance correction to handle the small number of clusters [63]. Models will include indicator variables for calendar time period to control for trends in HIV incidence in the study area.

We will compare baseline characteristics between individuals in the observation and intervention groups, using Chi-square or Fisher exact tests for categorical variables and Student t tests or Mann-Whitney U tests for continuous variables. Where imbalances are identified, we will control for these potential confounders in secondary analyses using GEE models as above. We will also conduct exploratory analyses to identify predictors of the combined outcome (i.e., newly diagnosed acute or prevalent HIV-1) in the intervention group, including age, sex, marital status, symptom or symptoms reported, sex of partners, number of partners, condom use, transactional sex work, and other risk behaviors. We will test for interactions between the intervention and other variables such as sex, and will present stratified analyses if meaningful interaction is observed. In analyses in which multiple null hypotheses are tested, p values will be adjusted using the Holm–Bonferroni method.

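### Section 8 says each facility is its own control, but the section 15.1 model draws about two-thirds or more of its information from comparing different facilities and omits the public/private randomisation stratum

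*Combined protocol and SAP*

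**What the plan says.** Section 8 (Study Design) has six facilities moving from observation to intervention in staggered three-month blocks, with 125 participants per facility per block. It states that each facility "will act as its own control, with comparison of those patients enrolled during the observation period to those patients enrolled during the intervention period". Facilities are assigned to rollout positions at random, "with stratification by facility type (public vs. private").

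Section 15.1 gives the primary model: individual-level log-binomial GEE, clustering by facility, and a small-sample variance correction. It adds: "Models will include indicator variables for calendar time period to control for trends in HIV incidence in the study area". It names no facility effect, no facility-type effect and no working correlation. Adjustment for imbalanced baseline characteristics is confined to secondary analyses and concerns characteristics of individuals.

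Section 14 assumes that "approximately 2% of young adults in this age range are diagnosed with prevalent HIV-1 infection under standard care" and that "approximately 5% will be newly diagnosed with acute (1%) or prevalent (4%) HIV-1 infection in the intervention period". With k = 0.25 it concludes: "we will have >90% power to reject the null hypothesis that the HIV diagnosis rates for experimental and control subjects are equal". The table entry for that case is 93.0%.

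**The concern.** If each facility were its own control, stable differences between facilities in HIV yield would drop out of the effect estimate. The planned model does not do this. Each facility is open for only three or four of the eight blocks, always observation first and intervention second, so its before–after change is closely aligned with calendar time. Once block indicators are in the model, most of what identifies the effect is a comparison of different facilities in the same block. In months 7–9, for example, sites 1 and 2 are on intervention while sites 3 and 4 are under observation.

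Two things follow. A reader of section 8 gets the wrong idea of where the evidence comes from and how robust it is to facility differences. And facility type, which the sponsor judged important enough to stratify on, bears directly on those between-facility comparisons yet is missing from the model. With six facilities, an uneven spread of types along the rollout order can move the estimate.

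**Working it through.** **Inputs.**
- Design (section 8, Figure 2): 23 facility-by-block cells of 125, of which 11 are observation (1,375) and 12 intervention (1,500). Site 1 runs O, I, I and sites 2–6 run O, O, I, I. Site 1's third block is inferred from the figure's column totals (250/375/500/500/500/375/250/125), which this layout matches.
- Rates (section 14): p0 = 2%, p1 = 5%, k = 0.25, type I error 0.05. Sidedness is not stated; two-sided reproduces the table.

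**Step 1: reproduce the plan's power.** Use generalised least squares on the 23 cell means, with eight block effects, an intervention effect and a random facility intercept.
- Mean rate: (0.02 + 0.05)/2 = 0.035.
- Facility SD: 0.25 × 0.035 = 0.00875.
- Cell variance: 0.035 × 0.965/125 = 0.000270.
- SE of the effect: 0.00872.
- Power: Φ(0.03/0.00872 − 1.96) = Φ(1.48) = 93.0%.

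All eight rows of the section 14 table are recovered to within 0.1 point: 94.4, 93.0, 91.4 and 89.4% for 5.0%, and 82.2, 79.9, 77.3 and 74.6% for 4.3%. The stated power therefore comes from a model that uses between-facility information.

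**Step 2: make each facility its own control.** Keep the cells, variance and block effects, and replace the random intercept with five facility indicators.
- SE: 0.01547.
- Power: Φ(0.03/0.01547 − 1.96) = Φ(−0.02) = 49.2%. For 2% versus 4.3% it is 34.6%.
- Other assumptions for 2% versus 5%: 52% on the log scale, 51–52% in a simulated logistic model (3,000 runs), and 55% with cell-specific variances on the risk-difference scale. The range is 49–55%.

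**Step 3: share of information.** Within-facility share = (0.00872/0.01547)² = 0.318, so about 68% is between facilities. The between-facility share is 70% at k = 0.20, 63% at k = 0.35, and 64.5% on the log scale at k = 0.25.

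Under an independence working correlation the estimate is a weighted average of same-block differences between facilities. Months 0–3, 19–21 and 22–24 (250 + 250 + 125 = 625 participants) then contribute nothing, because all facilities open in those blocks are in the same condition.

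**Step 4: effect of leaving out facility type.** The weights from step 1, summed by site, are +0.245, +0.146, +0.041, −0.041, −0.146 and −0.245. They would all be zero if facility differences cancelled. Suppose one type yields d points more than the other, and assume a 3 + 3 split (section 8 allows 2–4 of each). The estimate moves by d times the summed weights of that type's sites.
- Types paired along the sequence (one of each in positions 1–2, 3–4 and 5–6): 0.04d to 0.14d. For example, sites 1, 3 and 5 give 0.245 + 0.041 − 0.146 = 0.140.
- One type in positions 1–3 or 4–6 (2 of 20 orders): 0.245 + 0.146 + 0.041 = 0.43d.
- Average over all 20 orders: 0.18d.

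The documents give no value for d. If type explains half the facility variance at k = 0.25, then (d/2)² = 0.875²/2 in points squared, so d ≈ 1.24 points. The shift is then at most 0.14 × 1.24 = 0.17 points if paired and 0.43 × 1.24 = 0.53 points if bunched, against a 3-point target difference.

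**Step 5: cost of adding type.** Add a type indicator to the step 1 model, with type explaining nothing. The SE rises 0.1–1.7% in 12 of the 20 orders and 5.8% on average. In the two bunched orders it rises 31% and power is 75%.

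**The case against.** The strongest reply is that nothing here is invalid. Facilities are randomised to positions, so same-block comparisons between them are randomised comparisons, and any type-related shift averages to zero over the randomisation. The GEE clusters on facility, and the random-intercept variance behind the 93.0% already includes facility-level variation. The own-control sentence can be read loosely, as saying only that every facility passes through both periods. All of this stands except the last part: the sentence describes a before–after comparison of a facility's own patients, and that is not what mainly drives the planned estimate.

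Three stronger readings are tempting and are not supported.
- *That power is really 49%, not 93%.* The 49% belongs to a facility-fixed-effects analysis that the protocol does not propose. The 93.0% is right for the model that generated it.
- *That the primary estimate is biased.* The shift in step 4 is chance imbalance for the order drawn. Purposive choice of the six facilities affects generalisability, not the randomised order.
- *That the shift could approach a full percentage point.* That needs both a bunched order and a d of about 2 points. With a 3 + 3 split, d = 2 alone implies a facility SD of 1.0 point, above the whole SD of 0.875 points assumed at k = 0.25. Stratification may also have been meant to prevent bunching, though section 8 does not describe the scheme.

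The cost side must also be stated fully: the order in which omitting type matters most is the one in which including it costs most.

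**Conclusion.** The concern holds as a mismatch between the design description and the analysis, together with an omitted stratification factor. It does not show a wrong power figure or a biased estimator. Under the random-intercept model that reproduces section 14, about two-thirds of the information is between facilities; under independence all of it is. The plan does not say which structure applies. A genuinely within-facility analysis would have about 49–55% power for 2% versus 5%. Conditional on the order drawn, leaving out type moves the estimate by 0.04d to 0.14d in paired orders and by up to 0.43d in the two most bunched.

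These figures rest on Figure 2 as reconstructed, equal cells of 125, a 3 + 3 split of types, and the normal approximation that reproduces the section 14 table. The size of d is an assumption throughout.

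**What to change.** 1. **Section 15.1:** add facility type, the randomisation stratum, as a fixed term in the primary model. It costs one parameter, with the SE increases given in step 5. Section 8 randomises before study initiation, so the exact cost for the order drawn can be computed and recorded before any outcome data are seen.
2. **Section 8:** replace the own-control sentence with a statement that the effect combines within-facility comparisons and randomised between-facility comparisons. **Section 15.1:** name the working correlation. Quote a within-facility share only for that choice: about one-third under an exchangeable or random-intercept structure at k = 0.25, and none under independence. This changes wording only.
3. **Optional:** report a facility-fixed-effects estimate as a named sensitivity analysis, labelled in advance as having about 50% power. At 2% an observation cell expects only 0.02 × 125 = 2.5 diagnoses, so specify a fallback link in case the log-binomial model does not converge.
4. **Section 15.3:** use the same type term in the partner models only if the number of index cases supports it. The Protocol Summary expects about 28 in the observation period and 75 in the intervention period, and no calculation here covers those models.

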9. STUDY POPULATION

9.1. Inclusion Criteria for the Stepped Wedge Trial

The stepped wedge trial of the HIV-1 RNA testing intervention will be carried out in 6 outpatient health facilities in an area with a high prevalence of sex work, among both men and women. While sex work and other high-risk sexual behaviors are not part of the eligibility criteria for the study, data on sexual risk behaviors will be collected from all eligible patients.

The eligibility criteria target young adults, in whom HIV incidence is highest in Kenya, and focuses on symptoms and signs compatible with AHI, identified through our previous work (reviewed in Section 6.4).

Eligibility criteria for participation in the stepped wedge trial include:

- age from 18-39 years;
- · not previously diagnosed with HIV infection; and
- a score ≥2 on our risk score algorithm to identify persons at higher risk for AHI, with scoring as follows:
 - o age 18-29 years (1),
 - o fever (1),
 - o fatigue (1),
 - o body pains (1),
 - o diarrhea (1),
 - o sore throat (1), and
 - o GUD (3).

Eligibility criteria for partners of newly diagnosed cases with prevalent or acute HIV include:

- age over 18 years; and
- not previously diagnosed HIV infection.

9.2. Exclusion Criteria for the Trial

Patients not meeting inclusion criteria or those who are not willing or able to participate (e.g., due to illness or time constraints, or at the discretion of the study clinician) will be excluded.

Individuals at high risk for IPV are excluded from the aPS intervention, but eligible for all other components of the study.

9.3. Eligibility Screening for the Trial

Eligibility screening will be carried out using the screening form in section 21.6. This form has a permission script that research staff will read to participants. For those who consent verbally to screening, staff will initial the form and complete verification and documentation of eligibility. Individuals who refuse screening or do not meet eligibility criteria will not be enrolled into the study. All screening data obtained prior to written consent will be verified after the consent is signed.

9.4. Inclusion Criteria for Staff

Interviews or focus groups will be held for up to 60 individuals who work in the 6 health facilities where the trial will take place (up to 10 participants per facility). These individuals can work for the facility in any role, but will be required to have the following

Novel HIV-1 RNA testing intervention to detect acute and prevalent HIV infection - Tambua Mapema Plus

characteristics in order to participate: 18 years of age or older, planning to remain with the facility for the duration of trial implementation at that site, and willing to provide views on the detection of acute HIV infection and the research carried out at the facility, including challenges to intervention scale-up.

Version 1.1 17 July 2018 Page **26** of **137**

10. INTERVENTIONS

10.1. Biomedical Interventions

- 10.1.1. Testing for Acute and Prevalent HIV Infection
 - During the intervention period, a blood sample will be obtained and tested for AHI using the *Xpert*® *HIV Qual* assay (Cepheid, Sunnyvale, California, USA), with testing conducted on-site at the health facility where the participant was recruited and enrolled. This assay has been found to be easy to use and feasible in a community-based facility with limited or no laboratory infrastructure [58].
 - For participants in whom HIV-1 RNA is detected, a laboratory technician will conduct rapid HIV-1 testing (currently Determine®, Abbott Laboratories, Abbott Park, Illinois, USA; and First Response®, Premier Medical Corporation, Kachigam, Nani Daman, India) in accordance with Kenyan HIV testing guidelines.
 - HIV test results will be provided to participants in real-time, with post-test counselling by research staff and detailed documentation of results.

10.1.2. ART and HIV Care per Kenyan Guidelines

- Participants in the HIV-1 RNA testing intervention who are newly diagnosed with
 acute or prevalent HIV will be invited to participate in the ART cohort based at the
 nearest KEMRI Research Clinic (the KEMRI HIV research program has active
 research clinics in Kilifi, where the KEMRI-Wellcome Trust headquarters and
 reference laboratory are located, as well as in Mtwapa, which is within a one-hour
 drive from Kilifi). A map of the KEMRI clinical sites is in the appendices (Section
 21.11).
- Treatment in the ART cohort will follow the most recent Kenyan MOH ART guidelines, with medications supplied by the Kenyan MOH through NASCOP.
- Concomitant medications, including co-trimoxazole prophylaxis and STI/STD treatment as needed, will be administered according to the most recent Kenyan MOH guidelines.
- Adherence will be monitored by pharmacy logs, pill counts, and multiple self-report measures.

10.1.3. PrEP and Risk Reduction Counseling per Kenyan Guidelines

- Partners of newly diagnosed patients in the intervention period will be asked to undergo HIV counseling and testing and, if seronegative, will be invited to participate in the PrEP cohort based at the nearest KEMRI Research Clinic (described below).
- PrEP administration and monitoring will follow WHO and Kenyan MOH guidelines.
- Medications will be supplied by Gilead through a contract agreement.
- Adherence will be monitored in all PrEP cohort participants by pharmacy logs, pill
 counts, and multiple self-report measures. In a subset of PrEP cohort participants,
 MEMS® electronic caps will be used as an additional measure of adherence.

10.2. Behavioral Interventions

- 10.2.1. HIV Counseling and Testing Messages
 - Standard HIV counseling and testing per Kenyan guidelines will be used in the observation period.
 - For participants diagnosed with acute HIV infection during the intervention period, counselors will provide additional counseling messages regarding the high likelihood of recent infection and need for confirmatory testing.
 - These individuals will be told of the high infectiousness that is usual during AHI, and the high risk of transmitting HIV to their sexual partners or, for pregnant women, their child in utero.

10.2.2. Counseling for ART or PrEP Uptake and Adherence

- All newly diagnosed individuals will be counseled to initiate ART for their own health and to reduce their risk of transmission to others.
- Counseling to promote the uptake of and adherence to ART for HIV-infected individuals and PrEP for HIV-uninfected individuals in serodiscordant relationships will be both informational and motivational.
- Counselors at the KEMRI clinics have been trained in motivational interviewing following a modified version of Next Step Counseling that has been used successfully in [name] ongoing study of adherence among HIV-positive MSM on the Kenyan coast (1R34MH099946).
- This counseling approach includes the identification of each individual's barriers
 and facilitators to pill-taking and uses interactive exercises to ask the patient to help
 think through the possible solutions to his or her specific adherence barriers [59].

Version 1.1 17 July 2018 Page **28** of **137**

11. PROCEDURES

An overview of the schedule of visit procedures for each study component (observation period participants, intervention period participants, partners, ART cohort, and PrEP cohort) is included in the Appendices. Presented below is additional information for visit-specific study procedures for each component of the study. Detailed instructions to guide and standardize all study procedures across sites will be provided in the SSP Manual.

11.1. Recruitment Process

- 11.1.1. Recruitment and assessment of study eligibility
 - Eligible subjects will be recruited from among young (18-39 years of age) adults who
 present to any of the six health facilities in our HIV testing network.
 - At each facility, we will aim to enroll 2-4 participants per day, for a minimum of 10 and maximum of 20 per week. Staffing schedules will be developed in collaboration with each health facility, with a goal to ensure that recruitment targets are attained and that a range of time periods (e.g., daytime, evening, weekend) are covered. While research staff are present at the facility, we will approach consecutive patients for screening.
 - After obtaining verbal permission from the patient, facility clinicians or research staff present in the clinical room will screen patients to determine eligibility and ask if they are willing to discuss participation with the research team after their consultation. The screening form to be used for this purpose is presented in appendix 21.6. This form includes a permission script to be read to potential screenees and a space for research staff to initial that verbal consent for screening was provided. If a patient refuses screening, sex and estimated age will be recorded and the rest of the form will be blank. No identifying information will be obtained from screenees. All screening outcomes (i.e., screening refused, screened out, screened in but refused participation, screened in and consented) will be documented using the screening form.
 - Facility clinicians will then provide symptom-directed treatment to patients as per standard care and current Kenyan guidelines.
 - Upon completion of the consultation, and before any HIV testing is conducted, patients who meet eligibility criteria will be approached by the research team and invited to participate in the study. Individuals recruited during the intervention period will be shown a brief 2-minute explainer video that presents the study rationale and overview in English or in Kiswahili (please see https://www.youtube.com/watch?v=C7A_AatfKr4&feature=youtu.be).¹
 - Patients will then be consented to the study by research staff. During the consent process, staff will explain the purpose and design of the study, taking care to inform patients that participation is voluntary and will not influence their access to diagnostic testing or care.
 - During the observation period, we will use a consent (Consent 1) that focuses on the CASI/CAPI collection of data, collection of data on tests performed during the clinic visit, and permission for a follow-up visit at 6 weeks if newly diagnosed with HIV infection by the clinic.

Version 1.1 17 July 2018 Page 29 of 137

¹ The script for this video was reviewed and approved by our three ethical review boards.

During the intervention period, we will use a consent (Consent 2) that informs
participants that diagnostic testing is offered as part of the study and may reveal a
diagnosis of acute or prevalent HIV infection. The intervention period consent will
therefore focus on testing for acute and prevalent HIV infection, CASI/CAPI
collection of data, and permission to discuss results and further research
participation options with individuals who are newly diagnosed with HIV infection
by the research team.

